### **3.3 Duration of study**

It is planned to enroll 128 patients based on about 6 patients enrolled each month; and the time for

enrollment is about 24 months; the minimum survival follow-up period is 3 years, and the total study period will last about 60 months.

### **3.4 Withdrawal of patient from study treatment**

#### **3.4.1 Withdrawal criteria**

##### **3.4.1.1 Withdrawal time and method**

Patients may withdraw from study treatment and evaluation at any stage of the study, for the following reasons:

Patients are free to withdraw voluntarily from the trial at any time, and future treatment is not affected;

The Investigator and the Sponsor deem that there are any safety reasons (adverse events);

The Investigator and the Sponsor believe that the patient is poor in compliance to study protocol;

Death;

Loss to follow-up;

Other situations where Investigator believes that the patient should withdraw from the study.

The Investigator deems that the patient should withdraw from the study in the following cases:

Patients receive antitumor therapy other than this study protocol during the treatment period;

Patients have severe allergic reactions to investigational drug, such as exfoliative rash or hypersensitivity reactions of grade 3 to 4;

There is any other serious adverse reaction that, in the opinion of the principal investigator or his or her designated study personnel, requires a discontinuation of treatment;

Patients have severe poor compliance;

The urine  $\beta$ -HCG test results of patients suggest pregnancy. Investigator should report this pregnancy as a clinical trial pregnancy report form;

Other diseases are complicating the study, which in the Investigator's opinion will significantly affect the assessment of the patient's clinical condition and require discontinuation of this treatment regimen;

Other malignancies requiring treatment occur;

Patients are lost to follow up;

Prohibited drugs or other substances that in the Investigator's opinion may cause toxic reactions or bias study results are used.

Icotinib is discontinued for more than 2 consecutive weeks due to adverse reactions.

Patient dies.

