Duration of study	It is planned to enroll 128 patients based on about 6 patients enrolled each month; and the time for enrollment is about 24 months; the minimum survival follow-up period is 3 years, and the total study period will last about 60 months.
Study Drug Dosage/Route of Administration/Regimen	
Group A (icotinib group): Patients start to receive oral icotinib 125 mg, tid, for 12 months after R0 resection of NSCLC, or discontinue treatment due to tumor recurrence or intolerance.
 
Group B (control group) Patients are followed up after R0 resection of NSCLC.

Study Procedure	
After patients have signed the informed consent forms (ICFs) and meet the inclusion and exclusion criteria, they will be randomly assigned to the icotinib group and the control group.
 
Patients need to be evaluated. The patients receive the visits once every 3 months during the dosing period, and once every 6 months for the survival follow-up until the disease recurrence or death.
 
The Investigator shall contact the patient, the patient's family, or the patient's current physician by phone at least once every 3 months after recurrence, to collect the long-term follow-up information on survival. Any patient who withdraws from study treatment for reasons other than recurrence (except patient's withdrawal of informed consent, loss to follow-up, death) should continue to receive the objective tumor evaluation every 6 months to collect the information on recurrence.

Safety	All patients who have received at least one treatment with study drug will be included as the effective population for safety analysis. The patient's physical examination results, vital signs, adverse events, and abnormal laboratory test results will be summarized. Adverse events should be reported and graded according to the NCI Common Terminology Criteria for Adverse Events (CTCAE) version 4.0.
Statistical Analysis	The sample size is 128 for the following considerations: based on previous studies, the 3-year DFS for stage IB NSCLC is about 60%, the hazard ratio (HR) is 0.5, the test power ( $1 - \beta$ ) is 80%, and the test level ( $\alpha$ ) is two-sided 10%; enrollment period of 24 months, and total study period of 60 months.

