#### **3.4.1.2 Withdrawal procedure**

For patients who withdraw from the study, the Investigator shall ask about the reasons for withdrawal and whether any adverse events occurred. If possible, the Investigator should visit and evaluate patients who withdraw from the study. The reason and date of withdrawal (date of last dose) must be documented on the case report form (CRF). Patients should return all remaining study drugs.

Upon withdrawal from the trial, if there is a new or worsening laboratory test result of CTC grade 3 or 4, the patient must undergo further testing and the results should be documented in the appropriate section of the CRF until the laboratory test result returns to CTC grade 1 or 2, unless the test result is unlikely to improve due to the disease itself. The Investigator shall document their comments on these cases in the CRF and in the medical record.

All study-related toxicities and SAEs at study discontinuation must be followed until they are resolved, unless, in the Investigator's opinion, the condition is unlikely to be relieved because of the disease itself.

After the patient discontinues study treatment, the Investigator shall track all existing or new AEs that occur within 30 days of the last dose of study drugs, and report all new AEs and SAEs that occur within this period of time ([SAE](#) must be reported to the Sponsor within 24 hours) and follow up until the adverse event is resolved as described above. If a patient dies during the trial or within 28 days after the trial, the Investigator shall document the cause of death in detail on the serious adverse event (SAE) report within 24 hours.

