### **3.5.5 Treatment compliance**

The dose and date of administration of icotinib taken for each course of therapy for each patient should be documented in the CRF. Reasons for delayed administration, medication reduction, or missed doses should also be documented in the CRF.

Patient compliance with treatment and regimen includes voluntary compliance with all aspects of the regimen, including compliance with therapeutic agents, compliance with all blood collections required for safety assessment, and compliance with regular follow-up visits. Patients who do not take their medications on time, or who do not cooperate with tests, or who do not return to the study on time may be excluded

from the study based on the assessment of the principal investigator. Patients who discontinue icotinib due to unimprovable adverse reactions that do not resolve even with optimal symptomatic and supportive therapy may be withdrawn from the study if the duration of discontinuation is longer than 2 weeks, after discussion with and consent from the principal investigator.

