All analyses for efficacy are based on ITT population.

The Safety Analysis Set will include all subjects who received at least 1 dose of study drug and have a safety record after drug administration.

Descriptive statistics will be defined for continuous variables as number (n), median, mean, minimum and maximum, and as frequency and percentage for categorical variables.

The Kaplan-Meier method [2] will be used to estimate the point estimates of 3-year DFS for each group. The difference in 3-year DFS between groups will be compared by the Z test. The median DFS and OS will be estimated by the Kaplan-Meier method and the differences between median DFS and OS will be compared by the log-rank test.

Hazard ratios and their 95% confidence intervals for treatment effects are estimated using Cox proportional hazards models [3].

Unless otherwise specified, all statistical analyses will be performed using two-sided tests with a significance level of 0.05. All statistical analyses will be performed using SPSS and R.

11 Variables

Month=365/12 days.

Year=365 days.

Time since diagnosis to randomization = date of randomization – date of initial diagnosis) +1.

The duration of treatment was calculated as the (last dose date – first dose date) + 1.

Duration in study (days) = last day of known to be alive – date of randomization + 1

Follow-up time (days for DFS) = date of recurrence (patient who had recurrence) or date of last follow-up – date of randomization + 1.

Follow-up time (days for OS) = date of death (patient who died) or date of last follow-up – date of randomization + 1.

12 Missing data

No imputations will be made for missing data. Patients who does not have relapse or death will be censored at last follow-up.

13 References

3. Cox D. Regression models and life-tables. *J Royal Stat Soc Ser B*. 1972; 34: 187-220.

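### The protocol conflicts with itself on whether patients withdrawn for toxicity or poor compliance keep having tumour evaluation; if they do not, Kaplan-Meier 3-year DFS on icotinib could be overstated.

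*Protocol*

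**What the plan says.** **Text that lets evaluation stop.** Protocol 3.4.1.1 opens with "Patients may withdraw from study treatment and evaluation at any stage of the study, for the following reasons". Its reasons include safety and poor compliance. A second list names cases in which the investigator considers that the patient should leave the study. These include severe allergy to the study drug, other serious adverse reactions that require treatment to stop, other antitumour therapy, and this one: "Icotinib is discontinued for more than 2 consecutive weeks due to adverse reactions". Protocol 3.5.5 says that patients who miss medication or tests, "or who do not return to the study on time may be excluded" from the study at the principal investigator's assessment. For long interruptions caused by adverse reactions, it says that patients "may be withdrawn from the study if the duration of discontinuation is longer than 2 weeks", with the principal investigator's consent. Protocol 3.4.1.2 covers what happens next: "If possible, the Investigator should visit and evaluate patients who withdraw from the study".

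**Text that keeps evaluation going.** Under Study Procedure, the synopsis says that a patient who withdraws from study treatment for a reason other than recurrence "should continue to receive the objective tumor evaluation every 6 months to collect the information on recurrence". The exceptions are withdrawal of consent, loss to follow-up and death.

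**Analysis.** SAP section 10 puts all randomised subjects in the ITT set and bases all efficacy analyses on it. It estimates 3-year DFS per arm by Kaplan-Meier and compares the arms with a Z test. SAP section 12 makes no imputation and adds: "Patients who does not have relapse or death will be censored at last follow-up". The SAP describes no sensitivity analysis for withdrawal.

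**The concern.** A site that follows 3.4.1.1 and 3.5.5 literally can stop imaging a patient because of toxicity or poor compliance. A site that follows the synopsis cannot. Under the first practice, a recurrence after withdrawal is not recorded and the patient is censored at the last contact. Kaplan-Meier then treats that patient as having the same future risk as those still under observation.

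That assumption is doubtful for a patient who has just lost the drug whose effect is being measured. Severe allergy to icotinib and an icotinib interruption of more than two weeks can occur only in the icotinib arm, so the censoring could also be unequal between arms. Keeping the patient in the ITT set does not recover a recurrence that nobody looked for. What is at stake is the primary estimate, in an open-label trial with about 64 patients per arm and no replacement of withdrawn patients (Protocol 3.4.1.3).

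**Working it through.** **1. The passages side by side**

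| Question | Protocol 3.4.1.1, 3.4.1.2, 3.5.5 | Protocol synopsis |
|---|---|---|
| What does the patient leave? | Treatment and evaluation, or the study | Study treatment |
| Tumour evaluation afterwards | Where possible | Every 6 months |
| Who is exempt? | Not stated | Consent withdrawn, lost to follow-up, died |

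Both sets of text cover a patient taken off icotinib for toxicity, and they give different answers.

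**2. The plan's own effect size (SAP section 5)**

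Inputs: 3-year DFS 60% on control and 77% on icotinib, HR 0.5, 5% dropout, 128 patients randomised 1:1. Check: 0.60^0.5 = 0.7746, and ln 0.77 / ln 0.60 = 0.51. The planned rates and the HR agree to rounding.

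**3. Bias if withdrawn patients have a different 3-year DFS**

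Let w be the fraction of the icotinib arm withdrawn and q their true 3-year DFS, with 77% over the whole arm. If they are censored near the start, Kaplan-Meier estimates the DFS of those who stay:

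s = (0.77 − w·q)/(1 − w), and bias = s − 0.77.

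| w | q | s | Bias (points) |
|---|---|---|---|
| 5% | 77% | 77.0% | 0 |
| 5% | 60% | 0.740/0.95 = 77.9% | +0.9 |
| 5% | 40% | 0.750/0.95 = 78.9% | +1.9 |
| 10% | 77% | 77.0% | 0 |
| 10% | 60% | 0.710/0.90 = 78.9% | +1.9 |
| 10% | 40% | 0.730/0.90 = 81.1% | +4.1 |

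Only w = 5% has a source (the SAP's dropout figure, which is not arm-specific). The 10% and the values of q are assumptions. q = 60% means that the whole benefit is lost. q = 40% is worse than the untreated projection and serves as a pessimistic bound. If censoring is at month 6 instead, KM = S_mix(0.5 y) × s^(2.5/3), where S_mix is the DFS of the whole arm at six months. At 10% this gives 78.5% (q = 60%) and 80.2% (q = 40%). At 5% with q = 60% the bias is +0.7. This variant gives withdrawn patients the worse hazard from day 0, while they are still on drug.

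**4. Bias if the hazard changes only after withdrawal**

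Exponential DFS: control hazard −ln(0.60)/36 = 0.01419 per month, icotinib half of that, 0.00709. A fraction f is censored at month 3 and then has hazard h. Kaplan-Meier gives 77.5%. The withdrawn patients' true 3-year DFS is exp(−3 × 0.00709 − 33h), and bias = f × (77.5% − that value).

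| Hazard after withdrawal | Their 3-year DFS | Bias, f = 5% | Bias, f = 10% |
|---|---|---|---|
| Unchanged | 77.5% | 0 | 0 |
| Control level | 61.3% | +0.8 | +1.6 |
| 1.5 × control | 48.5% | +1.4 | +2.9 |
| 2 × control | 38.4% | +2.0 | +3.9 |

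The two models agree: about 0 to 2 points at 5% and about 0 to 4 points at 10%.

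**5. Offset from the control arm**

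Steps 3 and 4 set informative withdrawal in the control arm to zero. Suppose instead that 5% of controls with 40% true 3-year DFS also leave near the start. The control estimate becomes (0.60 − 0.05 × 0.40)/0.95 = 61.1%, an overstatement of 1.1 points. Against +1.9 on icotinib, the bias in the difference falls to about 0.9 points (1.95 − 1.05).

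**6. Scale**

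The standard error of the planned difference with 64 per arm is √(0.60×0.40/64 + 0.77×0.23/64) = 8.1 points, so +0.9 is about 0.1 standard errors. For false positives, take both arms truly at 60% and censor 10% of the icotinib arm at month 3, with twice the stayers' hazard. Expected Kaplan-Meier on icotinib is 62.1%. The chance of a finding in its favour is about 8.0%, against 5% per side at the two-sided 0.10 level of SAP section 5.

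**The case against.** The best defence is that the protocol often uses withdrawal to mean stopping the drug. The heading of 3.4 refers to study treatment. Section 3.4.1.2 equates the withdrawal date with the date of the last dose. The study-withdrawal visit in 3.7.2 is triggered by stopping study drug, and the synopsis states the continuation rule outright. On that reading a patient stopped for toxicity stays under imaging and nothing is lost. This stands as evidence of probable intent, so loss of outcome data is one reading and not an established fact. It does not remove the conflict: 3.4.1.1 names evaluation explicitly, 3.5.5 speaks of exclusion from the study, and the end-of-treatment assessments listed in 3.7.2 include no tumour imaging.

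A reader might infer that these rules contradict the ITT principle as the SAP defines it. The documents do not support that. SAP section 10 includes all randomised subjects, and nothing removes withdrawn patients from that set. The weakness is in follow-up, not in the definition of the population.

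A reader might also infer that 3-year DFS on icotinib will be biased upward. That is not shown either. With an unchanged hazard after withdrawal the bias is zero for any fraction withdrawn. Several triggers (voluntary withdrawal, missed visits or tests, other antitumour therapy, another malignancy) can occur under observation too, and control patients in an open-label trial may leave for prognostic reasons.

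**Conclusion.** The point holds as an internal conflict with a possible effect on the primary estimate. Sections 3.4.1.1, 3.4.1.2 and 3.5.5 allow tumour evaluation to lapse where the synopsis requires it to continue, and the SAP has no safeguard if it lapses. Kaplan-Meier 3-year DFS on icotinib could then be overstated by about 0 to 2 points at 5% withdrawn or about 0 to 4 points at 10%, against the planned 17. If withdrawn patients simply return to the control hazard at the SAP's 5%, it is about 0.7 to 0.9 points.

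These figures assume that only icotinib patients are withdrawn, that withdrawal is early, and that all of those withdrawn lose imaging. The fraction at 10% and the outcome after withdrawal are assumptions that the documents do not supply. The conflict merits correction because the remedy is cheap and removes this source of bias for every patient who stays under evaluation.

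**What to change.** Reconcile Protocol 3.4.1.1, 3.4.1.2 and 3.5.5 with the synopsis:

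- Reword withdrawal or exclusion from the study and its evaluation as discontinuation of study treatment only.
- State that all randomised patients keep the tumour evaluation and survival follow-up already planned. Tumour evaluation ends at recurrence, and all follow-up ends at death, loss to follow-up or withdrawal of consent.
- Make 3.4.1.1 and 3.5.5 agree on interruptions longer than two weeks, which one lists as a case for withdrawal and the other leaves to discretion. Which treatment rule applies is for the sponsor and investigators to settle. No treatment-stopping rule is proposed here.
- Use one DFS censoring date. Protocol 3.6.1 uses the last imaging evaluation and SAP section 12 the last follow-up, which differ for a patient reached only by telephone.

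The cost is protocol and SAP wording plus a few follow-up scans that the synopsis already plans. The sample size does not change.

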#### **3.4.1.2 Withdrawal procedure**

For patients who withdraw from the study, the Investigator shall ask about the reasons for withdrawal and whether any adverse events occurred. If possible, the Investigator should visit and evaluate patients who withdraw from the study. The reason and date of withdrawal (date of last dose) must be documented on the case report form (CRF). Patients should return all remaining study drugs.

Upon withdrawal from the trial, if there is a new or worsening laboratory test result of CTC grade 3 or 4, the patient must undergo further testing and the results should be documented in the appropriate section of the CRF until the laboratory test result returns to CTC grade 1 or 2, unless the test result is unlikely to improve due to the disease itself. The Investigator shall document their comments on these cases in the CRF and in the medical record.

All study-related toxicities and SAEs at study discontinuation must be followed until they are resolved, unless, in the Investigator's opinion, the condition is unlikely to be relieved because of the disease itself.

After the patient discontinues study treatment, the Investigator shall track all existing or new AEs that occur within 30 days of the last dose of study drugs, and report all new AEs and SAEs that occur within this period of time ([SAE](#) must be reported to the Sponsor within 24 hours) and follow up until the adverse event is resolved as described above. If a patient dies during the trial or within 28 days after the trial, the Investigator shall document the cause of death in detail on the serious adverse event (SAE) report within 24 hours.

#### **3.4.1.3 Substitute of withdrawn cases**

There is no substitute of patients who withdraw early from the study.

### **3.5 Treatment plan**

#### **3.5.1 Treatment schedule**

The enrolled patients are randomized to a group treated with icotinib for 12 months or a control group. Patients of the icotinib group are administrated with 125 mg of icotinib orally, tid, for 12 consecutive months after surgery, or discontinued due to disease recurrence or intolerable toxic reactions, and the control group is merely followed up.

#### **3.5.2 Discontinuation of icotinib**

- Due to good tolerance when used alone clinically, icotinib generally does not need to be discontinued. As reported in the literature, the incidences of interstitial lung disease (ILD) in Eastern populations treated with gefitinib and erlotinib are 2-3% and 1-2%, respectively. The interstitial lung disease is not observed in the ICOGEN clinical study.
- Patients with interstitial lung disease usually present with acute dyspnea with cough, hypothermia, respiratory distress, and arterial oxygen desaturation. The symptoms can be severe and fatal in a short period of time. Radiological examination often shows pulmonary infiltrates or interstitial ground-glass opacities.
- The treating physician should closely monitor for signs of interstitial lung disease during treatment and interrupt icotinib therapy if the patient develops a new acute attack or progressive worsening of dyspnea or cough, and perform relevant tests immediately. When interstitial lung disease is confirmed, the drug should be discontinued and the patient should be treated accordingly.

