### **Study Process Footnotes**

- A. Complete medical history (including a complete medical and surgical history of all relevant diseases), demographics, history of prior surgery, combined medication, concomitant diseases, allergies, and history of smoking. In particular, the history of previous and current pulmonary disease and/or systemic disease involving the lungs (e.g., connective tissue disease) should be inquired.
- B. It must be negative for premenopausal women of childbearing potential. For a suspected pregnancy event during the trial, the pregnancy test must be repeated, and a positive result must be reported immediately.
- C. LVEF should be examined for an abnormal ECG with clinical symptoms.
- D. Vital signs including heart rate, blood pressure, respiratory rate, and body temperature.
- E. In case of any spontaneous ocular symptoms, new or worsening respiratory symptoms (e.g., cough, shortness of breath), immediate and appropriate medical assistance should be given to the patient. Any symptoms should be treated as clinical routine and, if they meet the definition, are also reported as adverse events or serious adverse events (SAEs). Adverse events are collected from signing of the informed consent of the patient. After the study is terminated, all unresolved adverse events or serious adverse events are to be followed until solved, unless the Investigator deems them unlikely to be relieved due to the patient's own disease. All new adverse events and serious adverse events within 30 days of the last dose of the study should be reported (serious adverse events should be reported to the Ethics Committee of the GASTO Research Center and the National Medical Products Administration within 24 hours), and followed up until solved as described above. The most severe level of toxic reaction within each course of treatment is recorded in the CRF.

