## **8. Safety Principles**

### **8.1 Precautions/warnings**

#### **Icotinib**

The common adverse drug reactions (ADRs) of icotinib are rash (39.5%), diarrhea (18.5%), elevated aminotransferase (8.0%), most of which are of grades I and II and usually occur within 1-3 weeks after medication. Usually the ADRs are reversible and can disappear automatically, and there is no need of special treatment.

Warnings and precautions for icotinib are as follows:

1. According to the literature, the incidence of interstitial lung disease (ILD) is 2-3% and 1-2% in the

Eastern population treated with gefitinib and erlotinib, respectively. Interstitial lung disease is not observed in the ICOGEN clinical study. Patients with interstitial lung disease usually experience acute dyspnea with cough, low-grade fever, respiratory discomfort, and unsaturated arterial oxygen. In a short period of time, the symptoms can become severe and cause death. Radiographic examination often shows pulmonary infiltration or interstitial ground-glass opacities.

During the treatment, the treating physician shall closely monitor the signs of interstitial lung disease; and if the patient develops a new acute attack or progressively worsening dyspnea and cough, the treatment with this product should be interrupted and relevant examinations should be performed immediately. When interstitial lung disease is confirmed, the drug should be discontinued and the patient should be treated accordingly.

High risk factors for ILD reported in the literature include smoking, poor performance status (PS  $\geq 2$ ), normal lung tissue coverage  $\leq 50\%$  on CT scan, and short time since the diagnosis of non-small cell lung cancer ( $<6$  months), preexisting interstitial pneumonia, older age ( $\geq 55$  years old), with heart disease. Patients with these high-risk factors should use this product for treatment with caution.

2. This product should be used with caution in patients with mild transient elevations of hepatic aminotransferases that have been observed in a small number of patients. Patients with moderately elevated aminotransferase levels or above need to suspend the drug, and monitor the aminotransferase until the increase is relieved or disappears, and the drug can be resumed (see [Administration and Dosage]).

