3. Seek medical attention immediately if the following conditions worsen: New acute or progressively worsening dyspnea, cough; severe or persistent diarrhea, nausea, vomiting, or anorexia.

4. Effects on the ability to drive and operate machines: During the treatment with this product, symptoms of fatigue may occur, and patients with these symptoms should be reminded when driving or operating machines.

Clinically significant drug-drug interactions may occur with icotinib (see the Instruction for Use of Icotinib).

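### The rule for pausing icotinib on suspected interstitial lung disease asks for either symptom in Protocol 3.5.2 but for both in Protocol 8.1

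*Protocol*

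**What the plan says.** Protocol 3.5.2 (Discontinuation of icotinib), within the treatment plan, instructs the treating physician to "interrupt icotinib therapy if the patient develops a new acute attack or progressive worsening of dyspnea or cough".

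Protocol 8.1 (Precautions/warnings), item 1, repeats the paragraph almost unchanged, but its trigger reads "if the patient develops a new acute attack or progressively worsening dyspnea and cough, the treatment with this product should be interrupted". Both sections then require immediate tests, and permanent discontinuation once ILD is confirmed.

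Two other places mention the same symptoms without giving a dosing rule:

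- Footnote E to the study flow chart says that, for "new or worsening respiratory symptoms (e.g., cough, shortness of breath), immediate and appropriate medical assistance should be given to the patient".
- Section 8.1, item 3, says "Seek medical attention immediately if the following conditions worsen: New acute or progressively worsening dyspnea, cough".

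The two main paragraphs also describe how ILD presents. Section 3.5.2 has "acute dyspnea with cough, hypothermia, respiratory distress, and arterial oxygen desaturation"; section 8.1 has "acute dyspnea with cough, low-grade fever, respiratory discomfort, and unsaturated arterial oxygen".

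**The concern.** This is one safety instruction written twice with different logic. Under 3.5.2, progressive worsening of either symptom is enough to stop dosing while tests are done. Under the literal text of 8.1, both must worsen. A physician who turns to the warnings section when a patient reports a steadily worsening cough without breathlessness, or the reverse, is not told there to pause the drug.

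It is an operative dosing instruction, and both sections say that ILD can become severe and fatal quickly. A pause rule is meant to catch the early picture, before the full syndrome develops, and that is where the two wordings part. The conflicting temperature signs add to the problem, because the physician is given different things to look for depending on which section is open.

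**Working it through.** The plan gives no figure to reproduce on this point. The check is a comparison of the two triggers, followed by a calculation for scale.

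**Trigger logic, each section read alone and literally**

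| Presentation | 3.5.2 | 8.1, item 1 |
|---|---|---|
| New acute attack | Pause | Pause |
| Progressive worsening of both symptoms | Pause | Pause |
| Progressive worsening of dyspnea only | Pause | No pause called for |
| Progressive worsening of cough only | Pause | No pause called for |

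The rules are nested: every case that triggers 8.1 also triggers 3.5.2. They diverge only in the last two rows. Section 8.1 does not say to continue dosing in those rows; it gives no instruction to stop.

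**Which section is the outlier.** Footnote E gives cough and shortness of breath as separate examples of respiratory symptoms needing prompt help. Item 3 of 8.1 lists dyspnea and cough without requiring both. Both texts treat a single symptom as enough to act on, which sits with 3.5.2. They call only for medical attention, though, so they do not settle whether the drug is paused.

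**Temperature sign.** Section 3.5.2 names an abnormally low body temperature and 8.1 a mildly raised one, in otherwise matching sentences. No reading makes these the same sign.

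**Scale**

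Inputs:

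- Total enrolment: 128 (Protocol 3.1; SAP 5).
- Allocation: 1:1 (SAP 3.2), so the icotinib arm is 128 / 2 = 64.
- ILD rate *r* for icotinib: not given. Section 3.5.2 says that "the incidences of interstitial lung disease (ILD) in Eastern populations treated with gefitinib and erlotinib are 2-3% and 1-2%, respectively", and adds "The interstitial lung disease is not observed in the ICOGEN clinical study". I assume *r* lies between 0% and 3%, which spans these figures.

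Expected ILD cases in the arm = 64 × *r*:

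| *r* | Expected cases |
|---|---|
| 0% | 0 |
| 1% | 64 × 0.01 = 0.64 |
| 2% | 64 × 0.02 = 1.28 |
| 3% | 64 × 0.03 = 1.92 |

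These are all ILD cases, not cases affected by the wording. Only those presenting with progressive worsening of one symptom, at a site relying on 8.1 alone, could be affected. Single-symptom episodes that turn out not to be ILD would also be handled differently under the two rules. They are not counted here, because the documents give no rate for them.

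**The case against.** The strongest reply is that the protocol does contain the safeguard. A site is bound by the whole document, and 3.5.2, which sits in the treatment plan under a heading about stopping the drug, already has the broader and safer rule. Because the rules are nested, obeying 3.5.2 breaches nothing in 8.1. Section 8.1 reads like product-label text, and its *and* can be taken as a loose list of symptoms to watch for. For harm to follow, a site must use 8.1 alone, read the conjunction strictly, and meet a patient with a single symptom that worsens gradually. Both sections describe the usual presentation as acute breathlessness together with cough, which triggers a pause under either wording. Even a reader of 8.1 alone is told to monitor closely for ILD and to have worsening symptoms seen at once.

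Most of this stands, and it is why the point is minor. It does not remove the discrepancy. Nothing says that 3.5.2 prevails, the instructions to seek help are not instructions to pause, and a warnings section is a natural place to look when symptoms appear.

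It is also fair to say that the temperature conflict is a separate matter and looks like a translation slip. The background section has similar slips in drug names. The *and* may have the same origin, but the documents cannot show that. Either way the current text needs correcting. Finally, the ILD arithmetic does not measure the effect of the wording; it only shows that the numbers involved are small.

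**Conclusion.** The inconsistency is real and minor. For progressive worsening of one symptom, 3.5.2 orders a pause and 8.1, read alone and literally, does not. Section 8.1 is the one to correct. The descriptions of ILD in the same two paragraphs also contradict each other on temperature.

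The reach is small and cannot be put as a number of patients. The range of 0 to 1.9 expected ILD cases among about 64 treated patients rests on the assumption that icotinib's rate falls between the zero seen in ICOGEN and the upper gefitinib figure, and only part of that range could be affected. The conclusion about the wording depends on no numerical assumption. There is no consequence for type I error, power, sample size or endpoint capture.

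**What to change.** In Protocol 8.1, item 1, replace *and* with *or* between the two symptoms, or delete the trigger there and refer to 3.5.2 for the pause rule. A cross-reference has the advantage that the rule is then stated only once. In the same amendment, check the temperature sign in both paragraphs against the source text and make them agree.

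The cost is a wording amendment, with no new visits or scheduled tests. A site that had followed 8.1 literally might see a few more short interruptions, with the tests that 3.5.2 already requires. A short pause does not in itself take a patient off study: Protocol 3.4.1.1 and 3.5.5 tie withdrawal for adverse reactions to interruptions of more than 2 weeks.
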